**6.6. Safety Analysis**

**6.6.1. Study Treatments**

**6.6.1.1. Extent of Exposure**

Extent of exposure will be summarized, variables include: duration of treatment, number of cycles, total dose administered, dose intensity, and relative dose intensity for the entire treatment duration as well as for cycles if appropriate. Relative dose intensity (%) will be summarized using the following categories: <50%; 50% to <80%, 80% to <100%, ≥100%. Number and percentage of patients experiencing dose modification for each treatment arm and reasons will be provided.

The key parameters used to calculate dosing are shown in [Table JZGC.6.2](#).

**Table JZGC.6.2. Study Treatment Administration: Definition of Parameters**

	AM0010	Pembrolizumab
Dosing schedule per protocol	0.8 mg for ≤ 80 kg body weight 1.6 mg for >80 kg body weight Daily dosing	200 mg every 21-day cycle
Duration of treatment (months)	(last dose date – first dose date + 1) / 30.4375	
Number of Cycles	Count as a cycle when administered with pembrolizumab	When pembrolizumab administered
Cumulative Dose (mg)	Sum of the actual doses administered to a patient during the treatment period (not including cross over period)	Sum of the actual doses administered to a patient during the treatment period (not including cross over period).
Dose Intensity (mg/week)	mg received in a week cumulative dose / (duration of treatment / 7)	mg received in a cycle cumulative dose / total number of cycles
Relative Dose Intensity (%)	Actual dose intensity / planned dose intensity	

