**6.6.1.2.2. Pembrolizumab**

Pembrolizumab dose reductions are not permitted. A dose will be considered as actually delayed if the delay is exceeding 3 days (ie,  $\geq 4$  days from scheduled dosing date). Number of dose delays per patient, length of delay, and reason for delay will be summarized.

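### SAP Table JZGC.6.2: AM0010 dose intensity divides a duration in months by 7, and pembrolizumab dose intensity is per administered cycle, so its relative dose intensity cannot show delays

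*SAP*

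**What the plan says.** All the definitions are in SAP Table JZGC.6.2.

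- Duration of treatment has one entry for both drugs, in months. Its formula ends "first dose date + 1) / 30.4375". SAP 6.1.2 sets one month at 30.4375 days. The table defines no duration in days.
- Dose intensity is one row headed mg/week. For AM0010 the formula is "cumulative dose / (duration of treatment / 7"). For pembrolizumab it is "cumulative dose / total number of cycles", described as the mg received in a cycle.
- A pembrolizumab cycle is counted "When pembrolizumab administered".
- RDI is "Actual dose intensity / planned dose intensity". Planned intensity is not written out. It has to be inferred from the schedule row: 0.8 or 1.6 mg daily for AM0010, by weight band, and "200 mg every 21-day cycle" for pembrolizumab.

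SAP 6.6.1.1 makes RDI a reported output: "Relative dose intensity (%) will be summarized using the following categories", namely <50%, 50% to <80%, 80% to <100% and ≥100%. Protocol 10.6.5 also names RDI, for the whole treatment period and for each cycle. SAP 6.6.1.2.2 states "Pembrolizumab dose reductions are not permitted" and summarizes the number, length and reason of delays separately. SAP 6.6.1.2.1 does the same for AM0010 schedule reductions and withholds.

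**The concern.** The AM0010 cell has a unit error. Dividing by 7 converts days to weeks, but the only duration the table defines is in months. Days were evidently intended; the text does not say so.

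The pembrolizumab cell has a different problem. The quantity is mg per cycle under a mg/week header, and the denominator counts only cycles in which the drug was given. A delayed or withheld dose adds elapsed time but no cycle, so it leaves the measure unchanged. Because the dose may not be reduced, delay is the main way a patient still on treatment loses intensity.

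This is a randomized add-on design, so a natural exposure question is whether adding AM0010 costs patients some of their pembrolizumab. A pembrolizumab RDI that reads 100% for every fully infused patient in both arms cannot help answer it, and a reader could take it as evidence of full delivery. For AM0010, literal programming would make the four RDI categories useless.

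A smaller gap is that the unit of planned intensity is not stated, nor is its handling when a patient crosses 80 kg and the assigned AM0010 dose changes (Protocol 6.1).

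**Working it through.** The documents give no numerical dose intensity or RDI, so there is no figure to reproduce. The check evaluates the table's formulas on simple dosing histories.

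**AM0010, daily dosing.** Inputs: 0.8 mg daily for 84 days; planned 7 × 0.8 = 5.6 mg/week.

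- Cumulative dose: 84 × 0.8 = 67.2 mg.
- Duration as defined: 84 / 30.4375 = 2.7598 months.
- Intensity as written: 67.2 / (2.7598 / 7) = 170.45 mg/week.
- Intensity with days: 67.2 / (84 / 7) = 5.6 mg/week.
- Ratio: 170.45 / 5.6 = 30.4375, the same for any dose or duration.

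At 1.6 mg the cumulative dose is 134.4 mg, giving 340.9 mg/week instead of 11.2. Because the factor is constant, any true RDI of 100 / 30.4375 = 3.29% or more is reported as ≥100%.

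**AM0010, reduced schedules** (SAP 6.6.1.2.1), each followed for 12 weeks at 0.8 mg. The literal value uses the SAP's duration, which ends at the last dose. RDI is against 5.6 mg/week.

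| Schedule | Doses, mg | Last dose day | Literal mg/week | Literal RDI | RDI, days to last dose | RDI, days to next due dose (84) |
|---|---|---|---|---|---|---|
| 5 on/2 off | 60, 48.0 | 82 | 124.7 | 2227% | 73.2% | 71.4% |
| 4 on/3 off | 48, 38.4 | 81 | 101.0 | 1804% | 59.3% | 57.1% |
| 2 on/5 off | 24, 19.2 | 79 | 51.8 | 925% | 30.4% | 28.6% |

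All three literal values fall in ≥100%. With days, the first two belong in 50% to <80% and the third in <50%, under either way of ending the interval.

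**Pembrolizumab.** Inputs: six full doses, 6 × 200 = 1200 mg; planned 200 / 3 = 66.67 mg/week. As written, intensity is 1200 / 6 = 200 mg per cycle in every case, so RDI is 100% against 200 mg per cycle. If planned intensity took the header's unit, RDI would be 200 / 66.67 = 300% in every case. The elapsed-time version below uses (last − first + 21) days.

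| History | Days | mg/week | Elapsed-time RDI | RDI as written |
|---|---|---|---|---|
| On schedule | 105 + 21 = 126 | 66.7 | 100% | 100% |
| Every gap 28 days | 140 + 21 = 161 | 52.2 | 78.3% | 100% |
| One 84-day gap | 168 + 21 = 189 | 44.4 | 66.7% | 100% |
| One 105-day gap | 189 + 21 = 210 | 40.0 | 60.0% | 100% |

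The last two rows are two readings of a 12-week withhold: 84 days between doses (Protocol Table 4 counts from the last dose), or 84 days on top of the usual 21 (one reading of Protocol 6.4.1.2).

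**Last interval.** Reusing last − first + 1 for pembrolizumab would give 1200 / (106 / 7) = 79.2 mg/week, or 118.9%, for six on-time doses. A last-interval rule is therefore needed.

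**Weight-band change.** Take 42 days at 0.8 mg then 42 days at 1.6 mg, none missed: 33.6 + 67.2 = 100.8 mg over 12 weeks = 8.4 mg/week. Planned intensity averaged over the assigned dose is also 8.4, so RDI is 100%. Frozen at the starting band (5.6), it would be 150%.

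**The case against.** The intent for AM0010 is plain from the mg/week header, and a programmer would probably use days. A fully dosed patient at 3043.75% should be caught by any output check. If planned intensity were computed with the same months-based formula, the factor would cancel. All of this stands, so the extreme AM0010 figures show what the text says rather than what is likely to be reported. The definition still needs correcting.

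For pembrolizumab, the cell says it is mg per cycle and computes that, so one can call it a choice of measure under a wrong row label. Per-cycle reporting also fits Protocol 10.6.5. But whole-treatment RDI is planned too, and for that a measure blind to timing carries almost no information when doses cannot be reduced. Only an incomplete infusion could lower it.

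Delays are tabulated separately, and SAP 6.1.1 has all analyses presented by arm. That does answer the delay question more directly, and it limits the harm. It does not make the RDI table informative. Permanent discontinuation also reduces total exposure, but it appears in duration and number of cycles and is not what intensity measures.

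On the remedy, the last-interval and weight-band rules are conventions. The trailing off-days count in full only when the last dose falls on the last on-day of a block. Protocol 6.3 does not expressly list the date of a weight-band change among the recorded items. However, the SAP's cumulative dose already requires the actual doses given, and schedule adjustments are recorded.

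**Conclusion.** The point holds. As written, AM0010 dose intensity is overstated by a constant factor of 30.4375. Against 5.6 or 11.2 mg/week, this puts patients on every reduced schedule in ≥100%. Pembrolizumab RDI is 100% for any patient with full infusions, including histories whose elapsed-time RDI is 78.3%, 66.7% or 60.0%. The pembrolizumab defect matters more, because it would survive correct programming of the text.

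The AM0010 figures assume literal programming and a planned intensity in true mg/week. The pembrolizumab figures assume six full doses and a 21-day final interval. The consequences are confined to descriptive exposure tables; ORR, PFS, OS and the sample size are untouched. The table should be corrected, but the trial's conclusions on efficacy do not depend on it.

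**What to change.** In SAP Table JZGC.6.2:

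1. Compute dose intensity for both drugs in mg/week, with time in days and one last-interval rule: cumulative mg / [(date the next dose was due under the schedule in force at the last dose − first dose date) / 7]. For pembrolizumab the denominator is (last − first + 21) / 7. For daily AM0010 it is (last − first + 1) / 7. On a reduced AM0010 schedule, off-days that follow the last dose before the next due date count.
2. State planned intensity in mg/week. For pembrolizumab this is 66.7. For AM0010 it is 7 × the assigned daily dose, averaged over the days each weight-band dose was assigned, with toxicity schedule reductions not lowering it.
3. Keep months only for displaying treatment duration.

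The cost is two formula cells, one line defining planned intensity and the matching derivation code. No new data collection should be needed: Protocol 6.3 already records first and last AM0010 doses, withheld and missed doses and schedule adjustments. The derivation should confirm that weight-band change dates can be recovered from the dosing records. Pembrolizumab RDI will fall for patients with delays, as it should. A withhold never followed by another dose stays invisible in RDI, so a table footnote should direct readers to the separate withhold and delay summaries.

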**6.6.1.2. Dose Modifications**

**6.6.1.2.1. AM0010**

Dose schedule of AM0010 may be modified for toxicity. Dose schedule reductions are defined in the protocol as follows:

Dose Schedule	Schedule Modification Criteria	AM0010
SC QD (continuous daily dosing)	-	Starting dose schedule
5 Days on/2 days off	First Grade 3 or 4 event(s)	First dose schedule reduction
4 Days on/3 days off	Second Grade 3 or 4 event(s)	Second dose schedule reduction
2 Days on/5 days off	Third Grade 3 or 4 event(s)	Third dose schedule reduction

Parameters summarized include number and percentage of patient with at least 1 dose schedule reduction and reason for dose schedule reduction, number and percentage of patients with a dose schedule reduction to 5 days on / 2 days off, number and percentage of patients with a dose schedule reduction to 4 days on / 3 days off, and number and percentage of patients with a dose schedule reduction to 2 days on / 5 days off.

Number and percentage of patients with at least 1 dose withhold and reason for dose withhold will be summarized. Number of dose withhold per patient will be summarized as well.

**6.6.1.2.2. Pembrolizumab**

Pembrolizumab dose reductions are not permitted. A dose will be considered as actually delayed if the delay is exceeding 3 days (ie,  $\geq 4$  days from scheduled dosing date). Number of dose delays per patient, length of delay, and reason for delay will be summarized.

**6.6.2. Adverse Events**

Adverse event terms will be mapped using MedDRA. Adverse events will be graded according to the National Cancer Institute (NCI) – A Common Terminology Criteria for Adverse Events (CTCAE) v 4.03.

Pre-existing conditions are defined as AEs that begin prior to the first dose of study drug.

A treatment emergent adverse event (TEAE) is defined as any AE that begins between the day of first dose and 30 days after treatment discontinuation (or up to any time if serious and related to study treatment), or any pre-existing condition that increases in CTCAE grade between the day of first dose and 30 days after treatment discontinuation (or up to any time if serious and related to study treatment).

Related AEs in patients treated with AM0010 in combination with pembrolizumab are defined as either related to AM0010 or related to pembrolizumab or both AM0010 and pembrolizumab.

The following TEAE/serious adverse events (SAE) outputs will be produced:

- a. overview of TEAEs
- b. summary of TEAEs by Preferred Terms (PTs) (all grade and grade  $\geq 3$ )
- c. summary of TEAEs by System Organ Class (SOC) and PT (all grade and grade  $\geq 3$ )

- d. summary of TEAEs by PT and Maximum Grade
- e. listing of SAEs
- f. summary of SAEs by SOC and PT (all grade and grade  $\geq 3$ )
- g. listing of TEAEs leading to study treatment discontinuation

Summaries b, c, d, and f will be produced for the related TEAEs/SAEs.

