INTERIM ANALYSIS:	A planned interim analysis may be performed when the 50th randomized patient has been followed up for approximately 3 months. No statistical boundaries or alpha spending will be applied for this interim analysis as the primary purpose of this analysis is to assess safety and PK. At the time of interim data lock, all patients on study will continue on the study per protocol. See Table 6 for the schedule of analyses of key endpoints.
STATISTICAL METHODS: EFFICACY ANALYSES	All efficacy analyses will be based on the Intent-to-Treat (ITT) population, which includes all randomized patients regardless of whether the patient receives any study drugs or has any efficacy assessments. The primary efficacy endpoint is objective tumor response assessed according to RECIST v.1.1 criteria. The ORR will be summarized and compared using a Cochran-Mantel-Haenszel 2-sided test at a type I error rate of 10% stratified by tumor histology (squamous vs non-squamous.) Progression-free survival will be compared in the 2 randomized treatment arms using a 2-sided log-rank test, stratified by the tumor histology. Progression-free survival time will be summarized using the Kaplan-Meier method to estimate the median PFS and 95% confidence interval (CI). Overall survival will be summarized in the same manner as the PFS.
SAFETY ANALYSES	Safety Population includes all randomized patients who received any amount of study drug. Trial treatment exposure will be summarized. Adverse events will be summarized in terms of treatment-emergent events defined to be any event that begin or worsen in grade after first dose through 30 days after the last dose of trial drugs. Descriptive statistics of safety will be presented using NCI-CTCAE version 4.03 by treatment arm. All treatment-emergent AEs, due to any cause, treatment-related AEs, AEs leading to discontinuation from the trial treatments, SAEs, and drug-related SAEs will be tabulated using worst grade per NCI-CTCAE v4.03 criteria by system organ class and preferred term. On-trial lab parameters including hematology and chemistry will be summarized using the worst grade per NCI-CTCAE v4.03 criteria.

Table of Contents

CLINICAL TRIAL PROTOCOL	1
CONFIDENTIAL INFORMATION	1
PROTOCOL APPROVAL PAGE	2
PROTOCOL ACCEPTANCE PAGE	3
SUMMARY OF CHANGES	4
PROTOCOL SYNOPSIS	7
TRIAL GLOSSARY	21
1.0 BACKGROUND AND RATIONALE	24
1.1 Non-Small Cell Lung Cancer	24
1.2 AM0010 Background	25
1.2.1 AM0010 Mechanism of Action	25

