3.5 End of Treatment/Follow-Up Period

End of Treatment Visit

After patients receive their last dose of AM0010 and/or pembrolizumab, there will be a 28-day (± 7 days) follow-up period, after which patients will return to the trial site to complete end of treatment assessments (Section 7.9). Then, follow-up will begin on Day 35 (± 7 days) after the last dose of trial treatment.

Follow-Up Period

During the extended safety observation period, all randomized patients will be followed for safety 60 and 90 days (± 7 days) after the last dose of study treatment and monitored according to the schedule of assessments (SOA; [Appendix A](#)).

During the long-term follow-up period, all randomized patients will be followed for OS every 9 weeks (± 7 days) during the first year from the 90-day follow-up visit, every 12 weeks (± 7 days) during the second year, and every 16 weeks (± 7 days) thereafter. The survival follow-up will be conducted until death or study completion, whichever is first, whether or not trial treatment was administered.

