- Tumor assessment for all randomized patients who discontinue the trial treatment before disease progression or patients randomized but not treated. Tumor assessment will be repeated every 9 weeks (± 7 days) during the study treatment and during the first year from discontinuation of the study treatment, every 12 weeks (± 7 days) during the second year, and every 16 weeks (± 7 days) thereafter, until study completion, disease progression, death or receipt of new anti-cancer therapy, whichever is first.
- Subsequent cancer treatments (all randomized patients).
- Any SAEs considered to be related to trial treatment >90 days post last day of trial treatment, follow until resolution.
- Date and cause of death (all randomized patients).

Scans will include head and CAPs and will be sent to the central imaging vendor for archiving. If clinical progression is suspected, all relevant clinical documentation is to be submitted to the IRR for archiving and possible assessment at a later date. If clinical progression is suspected, all relevant clinical documentation is to be submitted to the central imaging vendor.

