7.10 Follow-Up Period

During the extended safety observation period, all randomized patients will be followed for safety 60 and 90 days (± 7 days) after the last dose of study treatment and monitored according to the SOA ([Appendix A](#)).

During the long-term follow-up period, all randomized patients will be followed for OS every 9 weeks (± 7 days) during the first year from the 90-day follow-up visit, every 12 weeks (± 7 days) during the second year, and every 16 weeks (± 7 days) thereafter. The survival follow-up will be conducted until death or study completion, whichever is first, whether or not trial treatment was administered.

For patients who were randomized, but withdrew consent, survival (date of death) will be obtained by use of publicly available information.

The Investigator (or designee) will acquire the following information from patients who were randomized:

- Tumor assessment will be repeated every 9 weeks (± 7 days) during the study treatment and during the first year from discontinuation of the study treatment, every 12 weeks (± 7 days) during the second year, and every 16 weeks (± 7 days) thereafter. Tumor assessment will be repeated until study completion, disease progression, death, or receipt of new anti-cancer therapy for patients who were randomized, and not treated or discontinue treatment before disease progression, and do not withdraw consent.
- Subsequent cancer treatments (all randomized patients).
- Any SAEs considered to be related to trial treatment, follow until resolution.
- Date and cause of death (all randomized patients).

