8.0 REMOVAL AND REPLACEMENT OF PATIENTS

8.1 Removal of Patients

Patients have the right to withdraw from the trial at any time and for any reason without prejudice to his or her future medical care by the physician or at the institution.

Any patient who withdraws consent to participate in the trial will be removed from the trial immediately upon the date of request. The Investigator will make every effort to contact the patient and perform end-of-treatment procedures. Should a patient (or a legally acceptable representative) request or decide to withdraw from the trial, all efforts will be made to complete and report the observations as thoroughly as possible in addition to follow up for OS. All information should be reported on the applicable CRFs.

The patient who requests to stop trial treatment or has withdrawn from trial treatment because of the Investigator's or Sponsor's concern before completion of the protocol-specified treatment duration will be strongly encouraged to continue the schedule of trial observations, in addition to follow up for OS.

If the patient has withdrawn because of toxicities, the Investigator should arrange for the patient to be followed for a minimum of 90 days or until any drug-related toxicities resolve to grade 1 according to CTCAE Version 4.03, or return to the patients' baseline values, in addition to follow up for OS. All end-of-treatment procedures should be completed for such a patient.

Reasons for removal from investigational product or observation may include:

- Withdrawal of consent
- Administrative decision by the Investigator or Sponsor
- The patient's physician feels it is no longer in their best interest of the patient to continue on treatment.
- Require subsequent systemic anticancer therapy
- Pregnancy (report on Pregnancy Notification Worksheet/CRF)
- Ineligibility determined after enrollment
- Significant protocol deviation
- Patient noncompliance
- Adverse event (disease progression is not considered an AE)
- Progression of disease (clinical and/or radiological)
- Lost to follow-up

The reason for withdrawal, the date of administration of the final trial treatment, and the date of withdrawal should be recorded on the End-of-Treatment CRF.

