10.6.6 Adverse Events

Adverse events will be analyzed in terms of treatment-emergent AEs defined to be any AEs that begin or worsen in intensity after trial drug initiation through 90 days after the last dose of trial drug. All AEs will be coded based on MedDRA terms.

Descriptive statistics of safety will be presented using NCI-CTCAE v4.03 by treatment arm. All treatment emergent AEs due to any cause, treatment-related AEs, SAEs, treatment-related SAEs, and AEs leading to discontinuation from the trial treatments will be tabulated using the worst grade per NCI-CTCAE v4.03 criteria by system organ class and preferred

term. Additional summaries include AEs by intensity (Grade 1 to 4 or/and Grades 3 and 4). All AEs will be listed.

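### Treatment-emergent AEs run to 90 days after the last dose in Protocol 10.6.6 but stop at 30 days in the synopsis and in SAP 6.6.2

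*SAP*

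**What the plan says.** Protocol 10.6.6 analyses AEs "that begin or worsen in intensity after trial drug initiation through 90 days after the last dose of trial drug". The Safety Analyses part of the synopsis counts events that "begin or worsen in grade after first dose through 30 days after the last dose of trial drugs". SAP 6.6.2 defines a TEAE as "any AE that begins between the day of first dose and 30 days after treatment discontinuation". It applies the same limit to worsening of pre-existing conditions, and lifts it only for events that are both serious and related.

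Other protocol text bears on which window was meant:

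- Section 3.5 states that "all randomized patients will be followed for safety 60 and 90 days" after the last dose, and 7.10 repeats this.
- Section 8.1 requires patients withdrawn for toxicity to be "followed for a minimum of 90 days or until any drug-related toxicities resolve to grade 1".
- Section 7.2 has a separate follow-up item, "Any SAEs considered to be related to trial treatment >90 days post last day of trial treatment", and 9.3 sets a matching reporting rule for related SAEs after Day 90.
- Section 9.3 puts AEs of every grade after consent on the CRF and gives no 30-day cut-off.
- The itemised list in 7.10 is narrower: "Any SAEs considered to be related to trial treatment, follow until resolution".

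Protocol 10.6.6 also promises that "All AEs will be listed". SAP outputs a to g do not include that listing. SAP 6.1.2 defines the date of first dose, but neither last dose nor treatment discontinuation.

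**The concern.** The protocol contradicts itself, and the SAP departs from the protocol's statistical section. The SAP gives no reason, and its revision history does not mention the TEAE window. All three definitions are current text, so the point does not rest on the protocol's summary of changes.

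Safety and tolerability is a secondary objective. The tables at stake are SAP outputs a to d and the related-event versions of b to d. The TEAE summary by anti-drug antibody status in SAP 6.7.3 uses the same term. A related, non-serious Grade 3 event on Day 45 after the last dose is a TEAE under Protocol 10.6.6. Under SAP 6.6.2 it is not, if discontinuation is dated to the last dose. The undefined anchor adds a second problem: two programmers following the SAP could produce different tables from the same data.

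**Working it through.** No sample size, power or event figure is involved. The check compares the definitions and subtracts window lengths.

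**Definitions side by side**

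| Text | End of window | Anchor | After that |
|---|---|---|---|
| Protocol 10.6.6 | 90 days | last dose | not counted |
| Protocol synopsis | 30 days | last dose | not counted |
| SAP 6.6.2 | 30 days | treatment discontinuation (undefined) | counted only if serious and related |

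**Excluded window when the anchors coincide**

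90 - 30 = 60 days (Days 31-90), and 60/90 = 67% of the post-dose window in Protocol 10.6.6. In that interval 10.6.6 counts every new or worsened AE. The SAP leaves out non-serious AEs (related or not), unrelated SAEs, and worsening of pre-existing conditions unless serious and related.

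**Excluded window when discontinuation is dated d days after the last dose (d is an assumption)**

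The SAP window ends at Day 30 + d, so the excluded part is max(0, 90 - (30 + d)) = max(0, 60 - d).

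| d (days) | SAP window ends | Excluded days |
|---|---|---|
| 0 | Day 30 | 60 |
| 21 | Day 51 | 39 |
| 60 | Day 90 | 0 |
| 84 | Day 114 | 0 |

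The last row uses the 12-week maximum AM0010 withhold in Protocol Table 2 (12 × 7 = 84 days) as an outer case. There the SAP window runs past the protocol's.

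**Arm 2 crossover patients**

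SAP 6.7.4 censors their control-arm AEs at crossover. Assume pembrolizumab is given on schedule every 21 days with no hold. The last dose is then at most 21 days before the progression scan. Protocol 7.8.1 allows at most 21 days from scan to crossover. Post-dose time before censoring is therefore at most 21 + 21 = 42 days. Against a 90-day window the shortfall is at least 90 - 42 = 48 days. Against a 30-day window it is between 0 and 30 days.

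**What still reports the late events**

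SAP outputs e and f (SAEs) and the deaths listing in 6.6.3 are not limited to TEAEs. The wording of SAP 6.6.4 to 6.6.6 (consolidated, immune-mediated and special-interest AEs) does not limit those summaries to TEAEs either.

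**The case against.** The inconsistency itself is hard to dispute. The case on the other side is that 90 days is not clearly the right target and that the effect is modest.

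- **Support for 90 days is uneven.** Section 8.1 concerns follow-up of toxicities in patients already withdrawn for toxicity; it is not an onset window for new AEs. The Day-60 and Day-90 visits follow Appendix A, whose AE row cannot be read reliably in the copy reviewed, and 7.10 itemises only related SAEs. Appendix B marks AEs at 28, 60 and 90 days, but only for the continued-access period. This stands, and it is why collection must be confirmed first. It does not remove the conflict: if non-serious AEs are not collected to Day 90, Protocol 10.6.6 cannot be met from the data.
- **A 90-day table widens the follow-up difference between crossover patients and others.** This stands, and it is the reason to keep a 30-day table. The 42-day bound is not general: a dose 3 days late gives 24 + 21 = 45 days, and a pembrolizumab hold could lengthen it further.
- **Observed time may be shorter than 60 days.** Protocol 9.3 lets follow-up be shortened when new anti-cancer therapy starts, so 60 days is an upper bound on the observed time lost.
- **The anchor is nearly there.** SAP Table JZGC.6.2 already uses a last dose date for treatment duration, and Protocol 8.1 records both the final-treatment and withdrawal dates. This makes the repair easy, but SAP 6.6.2 still uses a different, undefined term.
- **67% is a share of calendar days, not of events.** True, and it should be read only that way.

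**Conclusion.** The concern holds. Protocol 10.6.6, the synopsis and SAP 6.6.2 give conflicting TEAE windows, and the SAP's anchor is undefined. If discontinuation and last dose coincide, 60 of the 90 post-dose days in Protocol 10.6.6 (67%) fall outside the SAP's TEAE summaries, except for events that are serious and related. With discontinuation dated d days later, the loss is 60 - d days, and nothing at d = 60 or more. On-treatment AEs are counted under every definition. Because the documents give no AE rates, the number of events affected cannot be estimated. The inconsistency is certain. That 90 days is the intended window is well supported by the safety visits and the post-Day-90 SAE rule, but it depends on non-serious AEs being collected that long. This should be corrected, but it does not threaten the primary analysis.

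**What to change.** Before data lock:

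1. Confirm from the original Appendix A and the CRF instructions that non-serious AEs are collected to Day 90. If they are not, reconcile the collection instruction with Protocol 10.6.6 as well.
2. Align SAP 6.6.2 and the synopsis with the 90-day window of Protocol 10.6.6, or state in the SAP why it differs.
3. Define the date of last dose in SAP 6.1.2 as the last dose of any study treatment (AM0010 or pembrolizumab, whichever is later), matching the existing first-dose definition. Use it as the anchor in all three texts.
4. Keep the censoring at crossover in SAP 6.7.4. Keep a 30-day TEAE table as supplementary, because post-dose follow-up differs less between crossover patients and others at 30 days than at 90.
5. Add the listing of all AEs to the SAP outputs.

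The cost is wording in the SAP and synopsis, one definition, one programmed window, one supplementary table and one named listing. AE counts will rise, and some late events will reflect progression or later therapy. Arm 2 crossover patients will contribute a shorter post-dose window (at most about 42 of 90 days under on-schedule dosing). The safety interim has already been run, so its TEAE tables may not be comparable with the new window; the documents do not show which definition it used.
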